	
d. Total bilirubin (TB) $\leq 1.5 \times$ institutional upper limit of normal (ULN); Patients with known Gilbert's disease who have TB $\leq 3 \times$ ULN may be enrolled)e. Aspartate transaminase (AST)/ alanine transaminase (ALT) $\leq 3 \times$ ULN. If patient has liver metastases, AST and ALT $\leq 5.0 \times$ ULN.f. Creatinine $\leq 1.5 \times$ ULNg. International normalized ratio ≤ 1.5. 
10. Fasting blood glucose ≤ 140 mg/dL and hemoglobin A1c $\leq 8.5\%$ (both criteria have to be met).
 
11. Cardiac ejection fraction $\geq 45\%$.
 
12. Women of childbearing potential must have a negative serum or urine pregnancy test (minimum sensitivity 25 IU/L or equivalent units of human chorionic gonadotropin [HCG]) within 14 days prior to the initiation of treatment and/or postmenopausal women must be amenorrheic for at least 12 months to be considered of non-childbearing potential. Women of childbearing potential (WOCBP) must agree and commit to the use of 2 highly effective methods of birth control throughout the duration of the study until at least 150 days following the last dose of study drug. Acceptable methods are defined as those that result, alone or in combination, in a low failure rate (i.e., less than 1% per year) when used consistently and correctly, such as surgical sterilization, an intrauterine device, or hormonal contraception in combination with a barrier method. Women using systemically acting hormonal contraceptives should add a barrier method. In certain countries (if permitted by law), WOCBP may agree to abide by heterosexual sexual abstinence during the time of participation in this study.
 
13. Male patients and their female partners of childbearing potential must agree and commit to use a barrier contraception (eg, condom with spermicidal foam/gel/film/cream/suppository) throughout the duration of the study until at least 90 days following the last dose of study drug, in addition to their female partners using either an intrauterine device or hormonal contraception and continuing until at least 90 days following the last dose of study drug. This criterion may be waived for male patients who have had a vasectomy > 6 months before signing the ICF.
 
14. Willing and able to comply with the protocol for the duration of the study including undergoing treatment and scheduled visits and examinations.

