5.3 Inclusion Criteria

Patients eligible for inclusion in this study have to meet all of the following criteria:

1. Histologically confirmed ER+ and/or PR+ advanced or metastatic solid cancer including ovarian cancer (cohort 1), endometrial cancer (cohort 2), or breast cancer (cohort 3). Cohort 3 will be enriched to include at least 7 patients naïve to any PI3Ki in Stage 1 and also in Stage 2. ER and/or PR positivity is defined as >10% immunohistochemical staining of any intensity.
2. Presence of one or more PI3K and/or PTEN alterations in tumor tissue. Genetic alterations will include *PIK3CA* gain of function mutations, *PIK3R1* loss of function mutations, *PTEN* loss of function mutations, and *PTEN* deletions.
3. Measurable disease per RECIST 1.1.
4. The patient (or legally acceptable representative, if applicable) provides written informed consent for the study.
5. Female or male ≥ 18 years of age on the day of informed consent signing.

Proprietary Information of MD Anderson

Protocol 2020-1241

19 October 2022

6. Patients have no available standard therapy known to prolong survival. For cohort 3 prior treatment with a PI3Ki and everolimus is not required. The patients with or without prior treatment with PI3Ki and everolimus will qualify for enrollment
7. Adequate archived tumor tissue for the analysis for PI3K and PTEN alterations if available.
8. ECOG performance status of ≤ 2 .
9. Adequate organ and marrow function as defined below:
 - a. Hemoglobin ≥ 9.0 g/dL
 - b. Absolute neutrophil count $\geq 1.5 \times 10^9$ /L
 - c. Platelet count $\geq 100 \times 10^9$ /L
 - d. TB $\leq 1.5 \times$ institutional ULN; Patients with known Gilbert's disease who have TB $\leq 3 \times$ ULN may be enrolled)
 - e. AST/ ALT $\leq 3 \times$ ULN. If patient has liver metastases, AST and ALT $\leq 5.0 \times$ ULN.
 - f. Creatinine $\leq 1.5 \times$ ULN
 - g. International normalized ratio ≤ 1.5 .
10. Fasting blood glucose ≤ 140 mg/dL and hemoglobin A1c $\leq 8.5\%$ (both criteria have to be met).
11. Cardiac ejection fraction $\geq 45\%$.

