12. Women of childbearing potential must have a negative serum or urine pregnancy test (minimum sensitivity 25 IU/L or equivalent units of human chorionic gonadotropin [HCG]) within 14 days prior to the initiation of treatment and/or postmenopausal women must be amenorrheic for at least 12 months to be considered of non-childbearing potential. Women of childbearing potential (WOCBP) must agree and commit to the use of 2 highly effective methods of birth control throughout the duration of the study until at least 4 months following the last dose of study drug. Acceptable methods are defined as those that result, alone or in combination, in a low failure rate (i.e., less than 1% per year) when used consistently and correctly, such as surgical sterilization, an intrauterine device, or hormonal contraception in combination with a barrier method. Women using systemically acting hormonal contraceptives should add a barrier method. In certain countries (if permitted by law), WOCBP may agree to abide by heterosexual sexual abstinence during the time of participation in this study.
13. Male patients and their female partners of childbearing potential must agree and commit to use a barrier contraception (eg, condom with spermicidal foam/gel/film/cream/suppository) throughout the duration of the study until at least 60 days following the last dose of study drug, in addition to their female partners using either an intrauterine device or hormonal contraception and continuing until at least 4 months following the last dose of study drug. This criterion may be waived for male patients who have had a vasectomy > 6 months before signing the ICF.
14. Willing and able to comply with the protocol for the duration of the study, including undergoing treatment and scheduled visits and examinations.

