6.6.1 Female Patients

Women in the following categories are not considered women of childbearing potential:

- Premenopausal female with 1 of the following:
 - Documented tubal ligation
 - Documented hysterectomy
 - Documented bilateral salpingectomy
 - Documented bilateral oophorectomy
- Postmenopausal female
Postmenopausal is defined as ≥45 years of age, with at least 12 months of spontaneous amenorrhea.

Female patients of childbearing potential are eligible to participate if they agree to use a highly effective method of contraception consistently and correctly, as described in **Table 17** during the protocol-defined timeframe.

Table16: Highly Effective Contraception Methods

• Combined (estrogen and progestogen-containing) hormonal contraception
○ Oral○ Intravaginal○ Transdermal

• Progestogen-only hormonal contraception
○ Oral○ Injectable○ Implantable

• Intrauterine devices and intrauterine hormone-releasing system

• Bilateral tubal occlusion (women)

Proprietary Information of MD Anderson

Protocol 2020-1241

19 October 2022

- Vasectomized partner

A vasectomized partner is a highly effective contraception method provided that the partner is the sole male sexual partner of the woman of childbearing potential and the absence of sperm has been confirmed. If not, an additional highly effective method of contraception should be used.

- Sexual abstinence (men and women)

Sexual abstinence is considered a highly effective method only if defined as refraining from heterosexual intercourse during the entire period of risk associated with the study treatment. The reliability of sexual abstinence needs to be evaluated in relation to the duration of the study and the preferred and usual lifestyle of the patient. Periodic abstinence (such as a calendar, symptothermal and post-ovulation methods, withdrawal (coitus interruptus), and the lactational amenorrhea method are not acceptable methods of contraception

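### The contraception table in section 6.6.1 accepts estrogen-containing methods for female patients who have ER+ and/or PR+ cancer and are being treated with an estrogen-receptor antagonist

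*Combined protocol and SAP*

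**What the plan says.** Section 6.6.1 sets the rule for trial patients: "Female patients of childbearing potential are eligible to participate if they agree to use a highly effective method of contraception", with the acceptable methods listed in the table that follows. (The table is headed 16 and cited in the text as 17; the intended table is clear.) Its first entry is "Combined (estrogen and progestogen-containing) hormonal contraception", by oral, intravaginal or transdermal route. Section 6.6.2 refers to the same table for female partners of male patients, and the table does not separate the two groups.

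Inclusion criterion 12, in the synopsis and in section 5.3, requires that women of childbearing potential "must agree and commit to the use of 2 highly effective methods of birth control". It gives examples: "such as surgical sterilization, an intrauterine device, or hormonal contraception in combination with a barrier method". It adds: "Women using systemically acting hormonal contraceptives should add a barrier method". It says nothing on estrogen content.

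The population is defined by inclusion criterion 1: "Histologically confirmed ER+ and/or PR+ advanced or metastatic solid cancer". Section 1.2 describes fulvestrant as a competitive ER antagonist that degrades the receptor and has no estrogen agonist activity of its own.

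Section 6.4.1 prohibits hormone therapy when it is given as cancer treatment. It also lists herbal CYP3A4 inducers and grapefruit, but has no entry for estrogen.

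**The concern.** The trial gives a drug whose purpose is to block and degrade the estrogen receptor, in patients selected for hormone-receptor expression. The contraception table then names an estrogen-containing product as acceptable for those same patients. This is a stated permission that runs against the trial treatment, not a missing detail.

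At stake is an avoidable added estrogen exposure in women whose tumours may be estrogen-responsive. Section 6.4 also sends concomitant medication to the electronic medical record and not to the eCRF. If some women did use a combined method, that might not be visible in the trial dataset when responses are analysed.

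**Working it through.** No power, alpha or event count enters this point. The check sets the relevant sections side by side and then counts methods.

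**Does the permission apply to patients?** Yes. The table stands under the heading for female patients, and 6.6.1 ties their eligibility to it. Its second use, for partners of male patients in 6.6.2, does not change that.

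**Does criterion 12 repeat the permission?** Only by silence. It refers to hormonal contraception in general. The 6.6.1 table is the only place that names estrogen.

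**Does another section withdraw it?**
- Section 6.4.1 limits its hormone ban to cancer treatment, so contraceptive use falls outside it.
- Exclusion 3 is a washout for chemotherapy and other investigational therapy, not for contraceptives.
- Exclusion 9 lets the treating investigator exclude a patient because of a confounding therapy, or because taking part is not in her best interest. It is discretionary and does not name hormones.
- Section 6.4 ties concomitant medication to investigator discretion and community standards of care.
- Sections 4.1.7 and 6.9 let the investigator stop treatment or withdraw a patient.

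None of these removes the named table entry.

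**How many methods are affected?** The 6.6.1 table has 6 groups: combined hormonal (3 routes), progestogen-only (3 routes), intrauterine, bilateral tubal occlusion, vasectomized partner, and abstinence.
- Estrogen-containing: 1 of 6 groups.
- After removal: 6 − 1 = 5 groups.
- Tubal occlusion is barely a real option, because "Documented tubal ligation" already takes a woman out of childbearing potential in 6.6.1. Usable groups before the change: 6 − 1 = 5. After the change: 5 − 1 = 4 (progestogen-only, intrauterine, vasectomized sole partner, abstinence).
- Criterion 12 asks for two methods, so pairs matter too. Treat abstinence as standing alone and ignore pairings with a barrier. Before the change, 4 groups give 4 × 3 / 2 = 6 pairs. After it, 3 groups give 3 × 2 / 2 = 3 pairs. These are raw counts; a pair of two hormonal products would be of little practical use.
- Criterion 12 names 3 examples. All 3 remain, the third narrowed to products without estrogen.

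**How many women?** The documents give no figure. Section 6.6.1 removes postmenopausal women and those with hysterectomy, bilateral oophorectomy, bilateral salpingectomy or tubal ligation. Only women of childbearing potential who choose a combined method are left. The number could be zero.

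**The case against.** The strongest case against is that the consequence is thin and safeguards exist. An exclusion criterion defeats eligibility even when the contraception condition is met, and the best-interest limb of exclusion 9 fits an estrogen concern well. No patient is required to use a combined method. Fulvestrant degrades the receptor as well as competing for it. Women of childbearing potential may have endogenous estrogen in any case. Parts of the treatment text in sections 4.1.2 and 6 are not shown, so any handling of ovarian function cannot be judged. Removing a method rated highly effective also has a price when both drugs can cause fetal harm (section 6.6).

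Much of this stands as a limit on importance. It does not remove the table entry: a general discretion does not cancel a specific permission, and endogenous estrogen is no reason to approve an avoidable further source.

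A further objection is that a line drawn at estrogen is arbitrary. Patients with PR+ and ER-negative tumours can enrol, and the receptor-competition argument reaches them less directly. Progestogens might be questioned in PR+ disease. The first part is a fair limit on the inference. On the second, the documents show no conflict between progestogen-only methods and fulvestrant comparable to an agonist set against its antagonist, so that choice is left to the sponsor.

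**Conclusion.** The point holds for the 6.6.1 table. It expressly accepts an estrogen-containing method for female patients although all of them have ER+ and/or PR+ cancer and receive an ER antagonist, and no visible section withdraws that permission. The entry is 1 of 6 method groups, and the number of women exposed is unstated and probably small. The conclusion rests on a mechanistic inference from section 1.2 and on the visible text only.

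Three stronger readings are tempting, and the documents do not support them:
- A reader might infer that criterion 12 itself accepts estrogen. It refers only to hormonal contraception; it fails to exclude estrogen but does not name it.
- A reader might infer that contraceptive estrogen would lower ORR or shorten PFS. No section says so, and the effect of adding it to any endogenous estrogen is unknown.
- A reader might infer that contraceptives belong on the 6.4.1 prohibited list. That section ends by withdrawing patients who need a prohibited therapy, so an entry there would create a new problem.

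This is a cheap improvement of low to moderate priority.

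**What to change.** 1. Add under the 6.6.1 table: *Estrogen-containing methods are not acceptable for female patients; a patient using one switches to another accepted method without a gap in contraception. They remain acceptable for female partners of male patients (6.6.2).*
2. For consistency, in criterion 12, in both the synopsis and section 5.3, write *non-estrogen-containing hormonal contraception*. The sentence on adding a barrier can stand.

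Leave the two-method requirement unchanged. Leave criterion 13 unchanged as well; it concerns partners ("in addition to their female partners using either an intrauterine device or hormonal contraception"). Do not add contraceptives to the 6.4.1 list. Whether to restrict progestogen-only methods or hormone-releasing intrauterine systems is a clinical decision for the sponsor.

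The cost is wording in 6.6.1 and in the two copies of criterion 12, with no new visit, test or eCRF item. The downside is that a few women must change method, with 4 usable groups instead of 5 from which to meet the two-method requirement. The switch must be continuous because of the fetal risk.

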6.6.2 Male Patients

Male patients of childbearing potential must use a male condom plus spermicide. In addition, if the male patient's female partner is of childbearing potential, she should use a highly effective contraception method, as described in **Table 17**.

6.7 Use in Pregnancy

If a patient inadvertently becomes pregnant while on study treatment, the patient will immediately be removed from the study. The investigative team will contact the patient at least monthly and document the patient's status until the pregnancy has been completed or terminated. The investigator must notify the sponsor and/or supporting company within 24 hours of awareness of any pregnancy occurring from study treatment initiation until 150 days after the last dose of study treatment. The outcome of the pregnancy will be reported to the sponsor and/or supporting company without delay and within 24 hours. Individual cases with an abnormal outcome such as death, abortion, congenital anomaly, or other disabling or life-threatening complications to the mother or newborn are considered as SAEs and should be reported using the SAE form. The study investigator will make every effort to obtain permission to follow the outcome of the pregnancy and report the condition of the fetus or newborn to the sponsor and the supporting company. If a male patient impregnates his female partner during the study or in 90 days after the last dose of the study treatment, the investigative team must be informed immediately, and the pregnancy reported to the sponsor and/or the supporting company. The study investigator will make every effort to obtain permission to follow the outcome of the pregnancy and report the condition of the fetus or newborn to the sponsor and/or supporting company.

6.8 Use in Nursing Women

It is not known if copanlisib, fulvestrant or their metabolites are excreted in human milk. Copanlisib and fulvestrant can be detected in rat milk if administered to lactating animals. Since

Proprietary Information of MD Anderson

Protocol 2020-1241

19 October 2022

many drugs are excreted in human milk, and because of the potential for serious adverse reactions in the nursing infant, patients who are breastfeeding are not eligible for enrollment.

6.9 Patient Withdrawal/Discontinuation Criteria

Patients may withdraw consent at any time for any reason or be dropped from the study at the discretion of the investigator should any untoward effect occur. In addition, a patient may be withdrawn by the investigator if enrollment into the study is inappropriate, the study plan is violated, or for administrative and/or other safety reasons.

A patient must be discontinued from the study for any of the following reasons:

- The patient or legal representative withdraws consent. Every effort will be made to determine why any subject withdraws from the study prematurely.

A patient must be discontinued from study treatment (but may continue to be monitored in the study) for any of the following reasons:

- The patient or legal representative withdraws consent
- Confirmed radiographic disease progression with the exception of patients who are benefitting from the study treatment in the opinion of the investigator, the patient is clinically asymptomatic, and continuation of study treatment is approved by the sponsor.
- Unacceptable toxicity
- An intercurrent illness that prevents further administration of study treatment
- Investigator's decision to withdraw the patient
- The patient has a confirmed positive serum or urine pregnancy test
- Non-compliance with study treatment or procedure requirements
- Initiation of new anticancer therapy including another investigational agent
- The patient is lost to follow-up. A genuine effort must be made to determine the reason(s) why a patient fails to return for the necessary visits. If the subject is unreachable by telephone, a registered letter, at the minimum, should be sent requesting him/her to contact the clinic
- Death
- Dose interruption that exceeds 4 weeks
- Administrative reasons

When a patient is permanently discontinued from receiving study treatment prior to study completion, all applicable activities scheduled for the final study visit should be performed at the time of withdrawal. The patient will continue to be followed for safety unless consent is withdrawn or the patient is lost to follow-up or initiation of a new anticancer therapy. Patients who discontinue for reasons other than disease progression will have post-treatment follow-up for disease status until PD, death, initiation of new anticancer therapy, withdrawal of consent,

Proprietary Information of MD Anderson

Protocol 2020-1241

19 October 2022

or lost to follow-up. After confirmed disease progression, each patient will be followed for survival status until death, withdrawal of consent, or lost to follow-up.

6.10 Length and End of Study

The study begins when the first patient signs the ICF. Patients will receive study treatment until disease progression, unacceptable toxicity, death, withdrawal of consent, or discontinuation from the study treatment for any other reason. There is no maximum number of cycles a patient may receive if, in the opinion of the investigator, the patient is benefiting clinically from the study treatment.

The overall end of the study is defined as the time point when the final analysis is completed after the data collection stops in all cohorts. Also, the investigator may decide to terminate the study at any time.

7 ASSESSMENT OF SAFETY

The investigator is responsible for ensuring that all AEs and SAEs that are observed or reported during the study are collected and reported to the sponsor, the FDA, and the institutional review board (IRB) in accordance with 21 Code of Federal Regulations (CFR) 312.32.

7.1 Safety Parameters

7.1.1 Definition of Adverse Event

The International Council on Harmonisation (ICH) Guideline for Good Clinical Practice (GCP) E6 defines an AE as “any untoward medical occurrence in a patient, or clinical investigation patient administered a pharmaceutical product and which does not necessarily have a causal relationship with this treatment”. An AE can, therefore, be any unfavorable and unintended sign (including an abnormal laboratory finding), symptom, or disease temporally associated with the use of a medicinal product, whether or not considered related to the medicinal product.

An AE includes but is not limited to any clinically significant worsening of a patient’s preexisting condition. An abnormal laboratory finding that requires an action or intervention by the investigator, or a finding judged by the investigator to represent a change beyond the range of normal physiologic fluctuation, should be reported as an AE.

AEs may be treatment-emergent (i.e., occurring after initial receipt of investigational product) or non-treatment-emergent. A non-treatment-emergent AE is any new sign or symptom, disease, or other untoward medical events that begin after the written informed consent has been obtained, but before the patient has received the investigational product.

Elective treatment or surgery or preplanned treatment or surgery (that was scheduled prior to the patient being enrolled in the study) for a documented preexisting condition, that did not worsen from baseline, is not considered an AE (serious or non-serious). An untoward medical

Proprietary Information of MD Anderson

Protocol 2020-1241

19 October 2022

event occurring during the prescheduled elective procedure or routinely scheduled treatment should be recorded as an AE or SAE.

The term AE is used to include both SAEs and non-serious AEs.

